Study Center(s)	Meridian Research, Inc. [name]						
	[name]						
Clinical Phase	1						
Indication	ADHD (Attention-deficit/hyperactivity disorder)						
Sample Size	4 – 6 subjects						
Treatment Duration	Screening can occur up to 6 weeks prior to dosing. A single dose of study medication will be administered on Day 1 and the final study procedures will take place on Day 2.						
Objectives	The objective of this study is to evaluate the plasma amphetamine concentration/time profile of DYANAVEL XR in preschool children with ADHD following a single 1 mL (2.5 mg) dose of DYANAVEL XR.						
Methodology	This is a Phase 1, open-label study in children with ADHD to investigate the pharmacokinetic profile of DYANAVEL XR over a 28 hour period following the administration of a single dose of 1 mL (2.5 mg) of DYANAVEL XR in children with ADHD. Up to 4 - 6 subjects are planned for enrollment, aged 4 to 5 years of age at the time of signing of the Informed Consent.						
	Subjects will be screened for participation in the study within 6 weeks prior to study drug administration. Medical history, physical examination including height and weight, baseline laboratory testing, 12-lead electrocardiogram (ECG), vital sign measurements, a diagnostic assessment using the K-SADS-PL to confirm ADHD diagnostic criteria are met and informed consent will be completed during the screening visit.						
	Subjects will be confined from the day of dosing to at least approximately 13 hours after dosing. Each subject will receive a dose of 1 mL (2.5 mg) of DYANAVEL XR, administered by the site study staff at Time 0 (Day 1). For pharmacokinetic analyses of d- and l-amphetamine, 9 blood samples will be collected in total from each subject. Samples will be collected at pre-dose Day 1 (Time 0 to -2 hrs.), and at 1, 3, 4, 6, 8, 10, 12 and 28 hours after dose administration. Time after dosing will begin when DYANAVEL XR is administered to the subject. The subjects may then be released to their parents/ guardians with instructions to return to the study center for the final 28 hour (+/- 2 hours) sample; or they may remain at the study site for the duration of the						

	study. Safety assessments will include monitoring of AEs and concomitant medications throughout the study and collection of vital signs prior to medication administration and 4 hours post dosing.
Inclusion Criteria:	 Subjects must meet all of the following criteria to be considered eligible to participate in the study: 1. Male or female aged 4 to 5 years at the time at the time of enrollment into this study 2. Body weight ≥ 28 lb. at screening visit 3. Diagnosed with ADHD by a psychiatrist, psychologist, developmental pediatrician, pediatrician, or an experienced licensed allied health professional approved by the Sponsor by using the DSM-5 criteria and supported by a structured Kiddie-Schedule for Affective Disorders and Schizophrenia-Present and Lifetime version (K-SADS-PL) interview, administered at the Screening Visit 4. Provide written informed consent (parent/guardian) prior to participation in the study
Exclusion Criteria:	 Subjects who meet any of the following criteria will be excluded from participating in the study: 1. Diagnosed with any DSM-5 active disorder (other than ADHD) with the exception of specific phobias, learning disorders, motor skills disorders, communication disorders, oppositional defiant disorder, elimination disorders, and sleep disorders 2. History of chronic medical illnesses including seizure disorder (excluding a history of febrile seizures), moderate to severe hypertension, untreated thyroid disease, known structural cardiac disorders, serious cardiac conditions, serious arrhythmias, cardiomyopathy and known family history of sudden death 3. Known history or presence of significant renal or hepatic disease, as indicated by clinical laboratory assessment (liver function test results ≥ two times the upper limit of normal, blood urea nitrogen, or creatinine). 4. Clinically significant abnormal ECG or cardiac findings on physical examination (including the presence of a pathologic murmur) 5. Use of the following medications within 30 days of dosing: MAOI - monoamine oxidase inhibitors (e.g., Selegiline, isocarboxazid, phenelzine, tranylcypromine) Tricyclic Antidepressants (e.g. Desipramine, protriptyline) 6. Use of the following medications within 3 days of dosing: Gastrointestinal acidifying agents (e.g., guanethidine, reserpine, glutamic acid HCl, ascorbic acid) Urinary acidifying agents (e.g., ammonium chloride, sodium acid phosphate, methenamine salts) 7. Use of atomoxetine within 14 days of dosing 8. Planned use of prohibited drugs or agents from the Screening visit through the end of the study. Medications used to support sleep may be acceptable

	 with the written approval of the Sponsor or Medical Monitor 9. Abnormal clinically significant laboratory test values at screening that, in the opinion of the Sponsor or Medical Monitor would preclude study participation 10. Known history of allergy/hypersensitivity to amphetamine or any of the components of DYANAVEL XR, heparin flush and topical anesthetics 11. Parent or guardian's inability or unwillingness to follow directions of the Investigator or study research staff 12. Any uncontrolled medical condition that in the opinion of the Sponsor or Medical Monitor would preclude study participation 13. History of significant illness requiring hospitalization, or surgery requiring anesthetics within 30 days of dosing.
Assessments:	 K-SADS-PL Adverse Events Electrocardiogram Safety Labs Physical Exam Vital Signs Medical History Concomitant Medications
Criteria for evaluation:	Pharmacokinetics : The pharmacokinetic parameters for the concentrations of d- and l-amphetamine in plasma will be determined for each subject receiving study medication.
Statistical methods:	 Sample size determination: The sample size for this study was powered per FDA instruction. 4 - 6 subjects aged 4 to 5 years will provide adequate power for a pharmacokinetic analysis. Study populations: Adverse events will be reported for all subjects once enrolled. Total and treatment-emergent adverse events will be reported. All subjects with sufficient plasma concentration data for estimating pharmacokinetic parameters will be included in the pharmacokinetic analyses. Pharmacokinetic analysis: Pharmacokinetic parameters will be summarized and no formal comparisons will be made. Pharmacokinetic plasma samples: All PK Plasma samples will be sent frozen to the analytical lab after the end of the study. Safety analysis: MedDRA, current version will be used to classify all AEs with respect to system organ class and preferred term.
Safety:	Adverse Event (AE) collection

TABLE OF CONTENTS

SPONSOR'S	SIGNATURE	2
INVESTIGAT	OR'S SIGNATURE	3
PROCEDURE	S IN CASE OF EMERGENCY	4
TABLE OF CO	ONTENTS	8
LIST OF ABB	REVIATIONS	. 11
1.0	INTRODUCTION	. 13
2.0	STUDY OBJECTIVE	. 15
3.0	INVESTIGATIONAL PLAN	. 16
3.1	Overall Study Design	. 16
3.2	Rationale for Study Design and Control Groups	. 16
4.0	SELECTION AND WITHDRAWAL OF SUBJECTS	. 18
4.1	Inclusion Criteria	. 18
4.2	Exclusion Criteria	. 18
4.3	Discontinuation of Subjects	. 19

10.5.7	Summaries of Pharmacokinetic Endpoints	35
10.5.8	Interim Analyses	35
11.0	DIRECT ACCESS TO PROCEDURAL DOCUMENTS	36
12.0	QUALITY CONTROL AND QUALITY ASSURANCE	38
13.0	ETHICS	39
14.0	DATA HANDLING AND RECORD KEEPING	12
15.0	REFERENCES	13
16.0	APPENDICES	14
APPENDIX B	PK SAMPLES PROCESSING AND HANDLING	45

LIST OF ABBREVIATIONS

Abbreviation	Definition
ADHD	Attention-deficit hyperactivity disorder
AE	Adverse event
AUC	Area under the concentration-time curve
$AUC_{0-\infty}$	Area under the concentration-time curve from Time 0 to infinity
AUC _{0-t}	Area under the concentration-time curve from Time 0 to last sampling time (t) with a quantifiable plasma drug concentration
AUC ₀₋₁₂	Area under the concentration-time curve from Time 0 to 12 hours after dosing
CFR	(United States) Code of Federal Regulations
°C	degrees Centigrade
C _{max}	Peak (maximum) observed plasma drug concentration
CRF	case report form
D	Day
DSM-5	Diagnostic and Statistical Manual of Mental Disorders, 5 th edition
ECG	Electrocardiogram
ER	extended release
°F	degrees Fahrenheit
FDA	(United States) Food and Drug Administration
GCP	Good Clinical Practice
Н	Hour
HCl	Hydrochloride
HR	Heart Rate
ICH	International Conference for Harmonization
IEC	Independent Ethics Committee
IRB	Institutional Review Board
K-SADS-PL	Kiddie-SADS Present and Lifetime Version
kg	Kilogram
L	Liter
m^2	square meters
MedDRA	Medical Dictionary for Regulatory Activities
mg	Milligram
min	Minute
mL	Milliliter
РК	Pharmacokinetic

Abbreviation	Definition
SAE	serious adverse event
t _{1/2}	terminal-phase elimination half-life
t _{max}	time to peak (maximum) observed plasma drug concentration
US	United States
USP	United States Pharmacopeia
WBC	white blood cell

1.0 INTRODUCTION

Amphetamine has been a well-established therapeutic agent for the treatment of Attention Hyperactivity Disorder (ADHD) for decades. Since the original amphetamine approval, various dosage forms have been approved for use:

- Immediate release (IR) dosage forms, oral solution and tablets.
- extended release (ER) dosage forms, capsules, and tablets with various release technologies

DYANAVEL XR is an extended-release oral suspension that contains 2.5 mg/mL amphetamine base. Drug-resin complexation is formed with the amphetamine and Sodium Polystyrene Sulfonate USP, an ion exchange resin. The extended release feature of the product is achieved by coating some drug/resin complexes with an extended-release coating. DYANAVEL XR contains approximately a 3.2:1 ratio of d-amphetamine compared to l-amphetamine.

The efficacy of DYANAVEL XR in the treatment of ADHD in children ages 6-12 has been established in a Phase 3 placebo-controlled laboratory classroom study: TRI102-ADD-001. ADHD symptoms in children on an individually optimized dose of amphetamine (range 10-20 mg/day) were significantly lower compared to symptoms experienced by children treated with placebo. Symptom control was demonstrated 1 hour after dosing and efficacy was observed through 13 hours beyond dosing. The effect size in this study was in line with effect sizes demonstrated for other psychostimulants tested in a similar study design. The adverse events in this study were expected for amphetamine treatment with respect for type frequency and severity of adverse event.

Study TRI102-PPK-200 was conducted in children ages 6 to 12 years old with ADHD to evaluate the single-dose (10 mg) pharmacokinetics of orally administered DYANAVEL XR. Following a single 10 mg oral dose of DYANAVEL XR in 12 pediatric subjects under fasting conditions, d-amphetamine and l-amphetamine peak plasma concentrations occurred at a median time of 3.9 and 4.5 hours after dosing, respectively. The mean plasma terminal elimination half-life of d-amphetamine was 10.43 (\pm 2.01 h) hours and the mean plasma terminal half-life for l-amphetamine was 12.14 (\pm 3.15 h) hours.

Study 2014-3401 was conducted in 29 healthy adult subjects in a crossover study under fasting conditions, following a single, 18.8 mg oral dose of DYANAVEL XR, d-amphetamine and l-amphetamine, the median (range) time to peak plasma concentrations (T_{max}) were 4.0 (2 – 7) hours after dosing and peak concentration (C_{max}) were 102% and 106%, respectively of the C_{max} of immediate-release (IR) mixed amphetamine salts tablets. The relative bioavailability of DYANAVEL XR compared to an equal dose of mixed amphetamine salts IR tablets is 106% of d-amphetamine and 111% for l-amphetamine.

See the DYANAVEL XR Package Insert for further information¹.

The present study will fulfill a part of the Phase 4 Commitments Tris Pharma has made to conduct the following FDA required post-marketing studies in children aged 4-5 years with ADHD:

- 2970-1 A single-dose, open-label pharmacokinetic study of DYANAVEL XR (amphetamine) extended-release oral suspension, in children aged 4 to 5 years with ADHD
- 2970-2 A randomized, double-blind, placebo-controlled, flexible-dose titration study of DYANAVEL XR (amphetamine) extended-release oral suspension in children aged 4 to 5 years diagnosed with ADHD.
- 2970-3 A one year Pediatric Open-Label Safety Study of patients aged 4 to 5 years diagnosed with ADHD treated with DYANAVEL XR (amphetamine) Extended-Release oral suspension.

2.0 STUDY OBJECTIVE

The objective of this study is to evaluate the plasma amphetamine concentration/time profile of DYANAVEL XR in children aged 4 to 5 years with ADHD following a single 2.5 mg dose of DYANAVEL XR.

These data will guide appropriate dosing in planned safety and efficacy studies with DYANAVEL XR in a preschool population with ADHD.

3.0 INVESTIGATIONAL PLAN

3.1 Overall Study Design

This is an open-label, single-dose study in 4 -6 pediatric subjects with ADHD and who are otherwise healthy. Subjects will receive a single 1 mL dose of DYANAVEL XR (amphetamine) Extended-Release oral suspension 2.5 mg/mL.

Pharmacokinetics will be assessed over a 28 hour period after the single dose. Subjects may be kept at the study site(s) overnight.

Subjects with ADHD aged of 4 to 5 years will be enrolled at up to 2 study sites. Subjects will be screened for participation in the study within 6 weeks before study drug administration. Medical history, physical examination including height and weight, baseline laboratory testing, 12-lead electrocardiogram (ECG), vital sign measurements, a structured diagnostic interview (K-SADS-PL), and informed consent will be completed during the screening visit.

All subjects currently taking an ADHD medication including all psychostimulants methylphenidate, d-methylphenidate, amphetamines or derivatives of any of these products; must not take these medications for 48 hours prior to dosing with study medication. The ADHD medication can be resumed after the 28 hour sample is taken on Day 2, the final day of the study. The investigator should direct all other approved daily medications (see concomitant medications).

Subjects will be confined at the study center prior to dosing until approximately 13 hours postdose, or may stay until the 28 hour blood sample per principal investigator discretion.

Serial blood samples will be collected from all subjects at predetermined time points. The pharmacokinetic parameters of interest will include peak (maximum) observed plasma drug concentration (C_{max}), time to C_{max} (t_{max}), area under the concentration-time curve (AUC) from Time 0 to last sampling time (t) with a quantifiable plasma drug concentration (AUC_{0-t}), AUC from Time 0 to infinity (AUC_{0-∞}), and terminal-phase elimination half-life ($t_{\frac{1}{2}}$).

3.2 Rationale for Study Design and Control Groups

This study will evaluate the pharmacokinetic properties of DYANAVEL XR, administered orally to pediatric subjects aged 4 to 5 years with ADHD. Objective pharmacokinetic measurements will occur over 28 hours post-dose as a primary endpoint; therefore, an open-label, single-dose study design will be used. Due to the pharmacokinetic focus of this study, no placebo control group will be used.

One age group of pediatric subjects will be included in this study. The children will be aged 4 to 5 years on the day of enrollment into this study. Subjects will receive a 1 mL (2.5 mg) dose of DYANAVEL XR.

Dose Rationale: The dose range of the final optimal dose in a recent pivotal Phase 3 study of DYANAVEL XR in the treatment of children aged 6-12 years with ADHD (n=108) (TRI102-ADD-001) was 10 mg/day to 20 mg/day. None of the 108 subjects enrolled in that study discontinued due to an AE. There were no SAEs, deaths or severe AEs reported. Dosing was initiated at 1 to 2 mL (2.5 to 5 mg)/day (investigator's choice) and was titrated in 1 - 4 mL (2.5

to 10 mg) increments every 4 to 7 days until an optimal dose or the maximum dose (20 mg/day) was reached. Subjects had to reach a final optimal dose between 10 to 20 mg/day, inclusive. No subjects discontinued the study due to inability to tolerate a 10 mg dose.

The mean final optimized dose was 15.4 or 0.47 mg/ Kg. According to the CDC Growth $Chart^2$, the expected weight range with 3rd and 97th percentiles for a pediatric population ages 4 - 6 years is 12 - 24 Kg. Considering the low and high end of the weights for children aged 4 to 5 years, a single dose of 2.5 mg translates to a weight-based dose ranging between 0.21 mg/Kg and 0.11 mg/Kg, less than half of the mean weight-based dose that was well-tolerated in the previous study in children aged 6 to 12 years. Therefore it can be concluded that a single 2.5 mg dose of DYANAVEL XR is expected to be safe and tolerable to pediatric subjects aged 4 to 5 years with ADHD.

Meals: The study will be conducted with meals, snacks and beverages provided ad lib. Rationale: In adult volunteers, DYANAVEL XR had no food effect. Blood draws can be difficult in children, especially when not well-hydrated. Food intake may help reduce emesis (common in children during fasting PK studies) and may reduce vasovagal responses during blood draws.

Timing of PK sample collection: The main goal is to limit samples on the day of dosing to no more than 8 samples (pre-dose plus 7 post-dose samples) in order to collect an adequate amount of data while keeping the study feasible to conduct. The following collection times have been selected to meet goals of adequate data collection and study feasibility: Pre-dose and 1, 3, 4, 6, 8, 10, 12, and 28 hours post-dose.

With the exception of the 0 (pre-dose) and the 28 hour sample, samples will be collected within ± 15 minutes of the scheduled post-dose time. The pre-dose sample may be collected up to 2 hours before dosing. The 28 hour sample may be collected within 2 hours of the scheduled time. Actual times will be recorded for all events, and any deviation outside the specified ranges must be clearly documented in the subject's case report forms.

4.0 SELECTION AND WITHDRAWAL OF SUBJECTS

4.1 Inclusion Criteria

A subject must meet all of the following inclusion criteria to be eligible to enroll in this study:

- 1. Male or female aged 4 to 5 years at the time of enrollment into this study
- 2. Body weight \geq 28 lb. at screening visit
- 3. Diagnosed with ADHD by a psychiatrist, psychologist, developmental pediatrician, pediatrician, or an experienced licensed allied health professional approved by the Sponsor by using the DSM-5 criteria and supported by a structured Kiddie-Schedule for Affective Disorders and Schizophrenia-Present and Lifetime version (K-SADS-PL) interview, administered at the Screening Visit (Visit 0)
- 4. Provide written informed consent (parent/guardian) prior to participation in the study

4.2 Exclusion Criteria

The presence of any of the following exclusion criteria precludes a subject from study enrollment:

- 1. Diagnosed with any DSM-5 active disorder (other than ADHD) with the exception of specific phobias, learning disorders, motor skills disorders, communication disorders, oppositional defiant disorder, elimination disorders, and sleep disorders
- 2. History of chronic medical illnesses including seizure disorder (excluding a history of febrile seizures), moderate to severe hypertension, untreated thyroid disease, known structural cardiac disorders, serious cardiac conditions, serious arrhythmias, cardiomyopathy and known family history of sudden death.
- 3. Known history or presence of significant renal or hepatic disease, as indicated by clinical laboratory assessment (liver function test results ≥ two times the upper limit of normal, blood urea nitrogen, or creatinine).
- 4. Clinically significant abnormal ECG or cardiac findings on physical examination (including the presence of a pathologic murmur).
- 5. Use of the following medications within 30 days of dosing:
 - MAOI monoamine oxidase inhibitors (e.g., Selegiline, isocarboxazid, phenelzine, tranylcypromine)
 - Tricyclic Antidepressants (e.g. Desipramine, protriptyline)
- 6. Use of the following medications within 3 days of dosing
 - Gastrointestinal acidifying agents (e.g., guanethidine, reserpine, glutamic acid HCl, ascorbic acid)
 - Urinary acidifying agents (e.g., ammonium chloride, sodium acid phosphate, methenamine salts)
- 7. Use of atomoxetine within 14 days of dosing.
- 8. Planned use of prohibited drugs or agents from the Screening visit through the end of the study. Medications used to support sleep may be acceptable with the written approval of the Sponsor or Medical Monitor.
- 9. Abnormal clinically significant laboratory test value at screening that, in the opinion of the Sponsor or Medical Monitor, would preclude study participation

- 10. Known history of allergy/hypersensitivity to amphetamine or any of the components of DYANAVEL XR, heparin flush and topical anesthetics
- 11. Parent or guardian's inability or unwillingness to follow directions of the Investigator or study research staff.
- 12. Any uncontrolled medical condition that in the opinion of the Investigator would preclude study participation
- 13. History of significant illness requiring hospitalization, or surgery requiring anesthetics within 30 days of dosing

4.3 Discontinuation of Subjects

4.3.1 Subject Withdrawal Criteria

Within the provisions of informed consent and good clinical judgment with respect to the subject's safety, every attempt should be made to have subjects complete the study. The following are possible reasons to terminate the participation of any subject from the study:

- Signs and symptoms of intolerance to the study medication not alleviated by dose reduction.
- A treatment-related, serious adverse event (SAE) is observed.
- The subject or parent/guardian is grossly non-compliant, as determined by the Investigator.
- Continued participation, in the opinion of the Investigator, is no longer in the best interest of the subject.
- The parent/guardian wishes to withdraw for any reason.

Subjects will be encouraged to adhere to the protocol and complete all required assessments for the study. A subject may also be discontinued from the study for any of the following medical and/or administrative reasons:

- At the discretion of the Investigator or Sponsor at any time
- Occurrence of a treatment-emergent AE or considerable worsening of an AE that represents an unacceptable risk to the subject and when continued participation in the investigational study is not warranted, in the judgment of the Investigator or the Sponsor. The Investigator must follow the subject until the AE resolves or satisfactorily stabilizes.

Any enrolled subjects desiring to discontinue prior to study completion should be encouraged to continue in the study and adhere to the protocol and subsequent regularly scheduled safety evaluations. Subjects who are discontinued outside of any scheduled visit will be encouraged to complete the final study visit at the time of withdrawal. A subject who withdraws following study drug administration will not be replaced.

4.4 Study Stopping Rules

This study may be discontinued at any time if, in the opinion of the Principal Investigator or the Sponsor, continuation of the study represents a significant medical risk to participating subjects.

5.0 STUDY SCHEDULE AND PROCEDURES

5.1 Study Schedule

Schedules of study procedures for overall study assessments and day-of-dosing assessments are provided in Appendix A: Table 2.

5.1.1 Screening

Before any study-specific procedures are performed, the parent/guardian must receive an explanation of all study procedures and parent/guardian must sign and date an Institutional Review Board (IRB) approved written informed consent. Potential subjects who give their informed consent (parent/guardian) will undergo a Screening period (up to 6 weeks) to determine eligibility. Exceptions for longer screening periods for children requiring specialist consultation in order to qualify may be approved as evidenced by written confirmation from the Sponsor or Medical Monitor.

During the Screening visit, the following activities will be performed:

- Parent/ guardian informed consent
- Review of inclusion/exclusion criteria
- Review of medical history
- Review of medication history
- Demographics (i.e., sex, age, race and ethnicity)
- Physical examination
- Body height and weight
- Blood pressure, pulse, respiratory rate, and temperature
- Resting 12-lead ECG
- K-SADS-PL
- AE assessment
- Concomitant medications assessment
- Laboratory Tests:

 Table 1: Laboratory Tests

Serum chemistry panel:	Hematology CBC:
Alanine aminotransferase	WBC - White blood cell count
Aspartate aminotransferase	RBC - Red blood cell count
Blood Urea Nitrogen	Hemoglobin
Creatinine	Hematocrit
Glucose	MCV - Mean cell volume
Gamma-glutamyl transferase (GGT)	MCH - Mean cell hemoglobin
	MCHC - Mean cell hemoglobin concentration
	RDW – Red blood cell distribution width
	Platelet count

A local laboratory will be used to analyze screening laboratory tests. Out-of-range laboratory results may be repeated at the investigator's discretion. If additional screening laboratory tests are required, the sponsor must be contacted for approval.

5.1.2 Day 1 & 2

Subjects will be confined from the day of dosing to at least approximately 13 hours post-dose. Each subject will receive a dose of 1 mL (2.5 mg) of DYANAVEL XR, administered by the site study staff at Time 0 (Day 1). The subjects may then be released to their parents/guardians 13 hours post-dose with instructions to return to the study center for the final 28 hour (± 2 hours) sample; or they may remain at the study site for the duration of the study, at the discretion of the Investigator.

The following assessments will be conducted on the day of admission (Day 1) for all subjects:

- Vital signs taken before dosing and 4 to 6 hours after dosing;
- Body height and weight
- AE assessment
- Concomitant medications assessment
- PK sampling, processing and storage

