16.0 APPENDICES

APPENDIX A - Schedule of Study Procedures

Table 2: Study Procedures

	Screening	Procedures To Be Performed									
Procedure	Visit (Within 6 Weeks of Day 1)	Day 1									Day 2
		Oh	1h	3h	4h	6h	8h	10h	12h	13h	28h
Informed Consent	X										
Physical Examination	X										
Clinical Laboratory	Х										
K-SADS-PL	Х										
Demographics/ Medical History	X										
Vital Signs	X ^a	X ^a			X ^a						
Height/Weight	Х	X									
12-Lead ECG	Х										
PK Blood Samples		X	Х	Х	Х	Χ	Х	Х	Х		Х
Study Drug Admin.		X									
Prior/Concomitant Medications	X	X	X	X	X	X	X	Х	Х	X	Х
Adverse Events	Х	X	Х	Х	Х	X	Х	Х	Х	X	Х

^a At Screening, vital signs will include BP, HR respiratory rate and temperature. On study Vital signs will include only BP and HR (average of triplicate measurements) ^b Send home per Investigator discretion.

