APPENDIX B: PK SAMPLES PROCESSING AND HANDLING

Sample Collection

The actual date and clock time of each sample collection will be recorded. Samples will be collected in pre-chilled, labeled 3 mL blood collection tubes containing K_2EDTA as the anticoagulant.

Blood will be collected by direct venipuncture or from an indwelling cannula, which will be placed in a vein of the subject.

The samples will be maintained in an ice bath for no more than 3 hours. If needed, the samples can be maintained in refrigerator conditions $(5\pm3C^{\circ})$ for up to 8 hours throughout sample collection and until further processing.

Sample Processing and Storage

Within 8 hours of collection, the blood samples will be centrifuged at room temperature for 10 minutes at 3000 rpm. Samples that are interrupted during centrifugation, disturbed during the separation process will be re-spun under the same conditions in an attempt to separated and obtain the maximum amount of plasma from each sample.

Following centrifugation, the plasma will be divided in 2 approximately equal aliquots, placed in labeled polypropylene tubes, and kept in an ice bath until storage at $-25\pm10^{\circ}$ C.

Within 60 minutes of centrifugation, the aliquot tubes should be stored at $-25\pm10^{\circ}$ C.

No more than 8 hours should elapse between blood draw and centrifugation and no more than 60 minutes should elapse after samples centrifugation and the freezing of the plasma samples.

Sample Shipment

Packing & Bundling

- 1. PMRI will provide the clinic site with the Blood Collection Tubes, Aliquot Tubes and labels to be used for this study
- 2. The labels will contain the following information:
 - Study #
 - Subject #
 - Sampling Time point
 - Aliquot #
- 3. Pack the samples in Ziploc bags as follows:
 - a. Bundle all the samples for an individual subject for a single aliquot –together with an elastic band in a small Ziploc bag
 - b. Label the bag with the study # and subject #
 - c. Put all bags in a larger Ziploc bag and label the bag noting the study # and subject numbers

Example: 2015-3778, Subjects 01, 02 and 03

Never combine both aliquots in a single bag.

4. The samples will be shipped within a week of sample processing; the storage conditions must be maintained until sample shipment ($-25\pm10^{\circ}$ C.)

Documentation

- 1. With each shipment, include an *Inventory (Bundling) Checklist* and a *PK Sample Shipment Memo*.

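### No blood pressure or heart rate reading is scheduled before a child may go home at about 13 h; the last one is then 7 to 9 h old (minor, cheap to fix)

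*Combined protocol and SAP*

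**What the plan says.** **Timing of vital signs.** Section 5.1.2 (Day 1 & 2) lists "Vital signs taken before dosing and 4 to 6 hours after dosing". The synopsis describes "collection of vital signs prior to medication administration and 4 hours post dosing". Section 5.1 says that the schedules for "day-of-dosing assessments are provided in Appendix A: Table 2", and that table marks vital signs at Screening, 0 h and 4 h only. A footnote to it limits on-study vital signs to BP and HR, each averaged over three measurements.

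**Release.** Section 5.1.2 continues: "The subjects may then be released to their parents/guardians 13 hours post-dose", to return for the 28 h sample, or they may stay on site until then at the investigator's discretion. Sections 3.1 and 5.1.7 agree, and a Table 2 footnote reads "Send home per Investigator discretion". No section makes release depend on a BP or HR reading.

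**What is done at 13 h and 28 h.** The 13 h column of Table 2 has two entries: prior/concomitant medications and adverse events. The 28 h column adds the pharmacokinetic sample but no vital signs.

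**Use of the data.** Adverse events are the only safety endpoint (section 10.2.2), and vital signs appear only in listings (section 10.5.4).

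**The concern.** The protocol treats 13 h as a decision point. It has its own column in the schedule, two checks are made, and the investigator chooses between sending the child home and keeping the child overnight. The measurement most directly tied to a stimulant's cardiovascular effect is not scheduled there. The investigator does have the pre-dose and the 4 h (or 4 to 6 h) values, but no current one. If the single post-dose reading was raised, nothing in the schedule calls for a second to show that it has settled.

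The adverse event check at 13 h does not fill this gap. A rise in BP or HR without symptoms is seen only if someone measures it. What is at stake is a modest safety margin for 4- to 5-year-olds leaving supervision. No study result is affected.

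Separately, the three texts do not give the first post-dose reading the same time.

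**Working it through.** **Step 1. Age of the last scheduled reading at release.** Inputs: release at about 13 h (section 5.1.2); reading at 4 h (synopsis, Table 2) or up to 6 h (section 5.1.2).

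- Taken at 4 h: 13 − 4 = 9 h.
- Taken at 6 h: 13 − 6 = 7 h.

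The plan states no figure of its own to reproduce here.

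**Step 2. Is the existing reading well placed?** Section 1.0 gives median times to peak of 3.9 h (d-amphetamine) and 4.5 h (l-amphetamine) in 12 children aged 6 to 12 given 10 mg fasting. A reading at 4 to 6 h is close to both.

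**Step 3. How large is the dose?** Section 3.2 compares 2.5 mg with the mean optimised dose of 0.47 mg/kg at ages 6 to 12. For weights of 12 and 24 kg it prints 0.21 and 0.11 mg/kg; direct division gives 2.5/12 = 0.208 and 2.5/24 = 0.104, a difference that does not matter here. The entry limit of 28 lb is 12.70 kg.

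- At 12.70 kg: 2.5/12.70 = 0.197 mg/kg, and 0.197/0.47 = 0.42.
- At 24 kg: 0.104/0.47 = 0.22.

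The dose is thus about 22% to 42% of that mean.

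**Step 4. Drug remaining (context only).** Section 1.0 states: "The mean plasma terminal elimination half-life of d-amphetamine was 10.43" (± 2.01) h; for l-amphetamine it gives 12.14 (± 3.15) h. Assume single-exponential decline from the median peak time, read the ± figures as standard deviations, and assume that ages 4 to 5 behave like ages 6 to 12. Then

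share of peak at time t = 2^(−(t − tmax)/half-life).

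| | 13 h, mean half-life | 13 h, half-life ± 1 SD | 6 h, mean half-life |
|---|---|---|---|
| d | 2^(−9.1/10.43) = 0.55 | 0.47 to 0.60 | 2^(−2.1/10.43) = 0.87 |
| l | 2^(−8.5/12.14) = 0.62 | 0.52 to 0.68 | 2^(−1.5/12.14) = 0.92 |

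Shorter half-lives in smaller children would lower these shares; continuing absorption would raise them. Roughly half of a low peak remains at 13 h. The documents give no relation between concentration and BP or HR, so this predicts no rise. The 6 h column shows that a reading at 6 h rather than 4 h is still near the peak.

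**Step 5. Is there room for readings?** Draws between 1 h and 12 h have a ± 15 minute window (sections 3.2 and 5.1.3.1).

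- 4 h draw: 3:45 to 4:15. 6 h draw: 5:45 to 6:15. The time from 4:15 to 5:45, 90 minutes, is free of draws.
- 12 h draw: over by 12:15, which is 45 minutes before 13 h. No draw is scheduled at 13 h.

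This spacing is useful because "Blood will be collected by direct venipuncture or from an indwelling cannula", and either may unsettle a young child.

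**The case against.** The strongest reply is that this is a preference and not a flaw. The objective is pharmacokinetic, no stated rule is breached, and BP and HR are measured where exposure should be highest. Release is already a clinical decision. Children are supervised throughout confinement, adverse events are checked at eight post-dose times up to 13 h, serious cardiac conditions and moderate to severe hypertension are excluded, and nothing prevents an unscheduled reading or a stay to 28 h. A required value without a threshold feeds the same discretion, may be distorted by fatigue, and becomes a deviation if missed.

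Most of this stands, and it is why the point is minor. What it does not answer is that discretion permits a reading without securing one for every child, and that a raised value at 4 to 6 h has no scheduled follow-up.

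A reader might go further and infer that children are being sent home at appreciable risk, because about half of the peak drug level is still present. The documents do not support that. They link no concentration to a BP or HR change, the peak itself is low, and they give no reason to expect a worse reading at 13 h than near the peak. Nor do the differing times amount to a conflict that harms the data. The range of 4 to 6 h can be read as an allowance around a nominal 4 h, actual times are recorded, and vital signs are only listed.

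**Conclusion.** The point holds as a minor, inexpensive improvement. The only scheduled post-dose BP/HR set is 7 to 9 h old when a child may leave, and no repeat is scheduled even after a raised reading. The size rests on the stated times alone and needs no pharmacokinetic assumption, except that release happens at about 13 h; a child kept longer without a further reading would have an older one. Serious harm is unlikely. The residual-drug shares are extrapolated from older children at a different dose and under fasting, whereas this study gives food freely, and no part of the conclusion depends on them. The mismatch in the first post-dose time is editorial and adds no weight. A 28 h reading is not needed to close this gap.

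**What to change.** 1. Add one triplicate BP/HR set at about 13 h, taken before release and reviewed by the investigator. Put it in all three places: the 13 h column of Table 2, section 5.1.2 and the synopsis. No new threshold is required, because the option to keep a child until 28 h already exists.
2. As an editorial alignment, state the first post-dose reading in the same three places as nominal 4 h with 4 to 6 h allowed. Leave it free within that range so that it can use the gap between the 4 h and 6 h draws. Tying it to the time before the 4 h draw would not work, since that draw may start at 3:45 and the reading could then fall before 4 h.

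**Cost.** Three cuff readings per child: 3 × 4 = 12 to 3 × 6 = 18 in total. That is a few minutes each at the end of a long day, possibly with some fussing that affects the value, and one more procedure whose omission must be handled as a deviation (section 13.7). It needs no extra visit, blood draw or staff.
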